4.2. [name], director of Sleep Medicine at the Phoenix VA, will refer subjects to the study, help diagnose and screen new cases, and supervise the assessment and scoring of the PSG recordings.

4.3. [name], BS, RD, is director of the Move! program at the Phoenix VA. In pioneering research of obese veterans (n=20) by [name] et al. (Food and Nutrition Conference & Expo, Houston, October 20, 2013),

a 6-16 week intervention involving behavioral counseling (as proposed here) and strict meal replacement elicited an average body weight reduction of 16%, and >20% for veterans who were in the program for over 6 weeks. Moreover, the intervention resulted in dramatic improvements in glucose regulation, lipids, and blood pressure; a decreased use of medicines; and postponement of knee surgery in some patients due to lowered pain. [name] will lead the weight loss interventions for the study. Moreover, [name], who also has extensive experience accomplishing weight loss, will serve as a consultant for the weight loss.

4.4. [name], is a biostatistician with expertise in statistical analysis of health behavior data. He will be working with [name] on an R01 project examining effects of chronic moderate sleep restriction in older long sleepers and average sleepers for which similar analyses of repeated measures data will be conducted. For the proposed project, [name] will provide guidance on data analyses and interpretation.

4.5. [name], a clinical psychologist (license pending) and sleep scientist, will provide counseling and/or immediate referral to participants who experience psychological difficulties during the experiment; assess potential disparities in OSA and in responses to the treatments; and facilitate minority recruitment.

5. Work Proposed

5.1. Timeline. The proposed 4-year randomized controlled trial will assess N=90 veterans (ages 18-60 years) with OSA. Each year, 22-23 participants will be assessed in 18-week cycles, including screening, baseline, and a 16-week intervention. Follow-up assessments will continue for 3 months after the intervention.

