Mediation Analysis. Possible mediating variables that could explain the reduction in OSA will be evaluated using MacKinnon’s product of coefficients test. Pre-specified potential mediators will include percent of NREM-3 (deep sleep), body weight, trunk body fat percentage, respiratory muscle strength, and upper airway obstruction (FIF₅₀/FEF₅₀). Each potential mediator will be tested in a single mediator model, to include (1) estimating the effect of the intervention on the potential mediator (i.e., α coefficient) by regressing the mediator’s post-intervention value on the intervention group while controlling for the potential mediator’s baseline value; (2) estimating the effect of changes in the mediator on changes in AHI (i.e., β coefficient) by regressing post-intervention AHI on the mediator’s post-intervention value, controlling for treatment group, baseline AHI, and the mediator’s baseline value; and (3) calculating the product of coefficients by multiplying the α and β coefficients. Coefficients will be obtained through linear regression models using SAS PROC GLM. Asymmetric confidence limits based on the distribution of the product of coefficients will be created using the PRODCLIN program; confidence intervals that do not include zero will indicate a significant mediation effect.

5.11. Process evaluation. An independent observer will assess study feasibility, fidelity of protocol delivery, and subject adherence. Participants will also complete a survey of barriers and benefits to study participation.

5.12. Timeline. The study will take 4 years. Equipment purchases will occur in the initial 2 months. With rolling admission, we will strive to schedule waves of ≥ 5 participants. Baseline assessments should begin by the end of Month 2, and baseline assessments of new waves of participants will occur monthly. Data collection is expected to take 44 months. Final analyses and manuscripts preparation will occur during the final 2 months.

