5.13. Potential Problems and Limitations of Methods. Excellent participant recruitment will be paramount. We previously assessed N=43 OSA subjects over 2 yr for consultant [name]’s dissertation. However, for the proposed study, we have a much closer association with Sleep Medicine at the VA. The director, co-investigator [name], interprets about 25 new cases of OSA per week. She and the staff can inform these patients about the study. We would need to recruit only 2% of these cases if this was our only source of subjects. We will also seek a HIPAA waiver to provide information about our study to the 30,000 Phoenix VA patients who have been diagnosed with OSA. Other factors that will benefit recruitment include an expanded subject age range (from 18-55 to 18-60 years of age); less stringent inclusion criteria; and having [name] as a consultant. If we still are unable to recruit enough veterans, we will request permission to include non-veterans.

Retention of participants will be critical for the success of the study, and sedentary and/or overweight individuals are high risk of drop-out or poor adherence to exercise. However, a run-in period will reduce the number of non-adherents, and personalized attention throughout the intervention should promote retention. For our previous study, only 5 of the 43 participants who began the intervention discontinued the study. Another benefit for retention is that the entire study will be conducted at the Phoenix VA, whereas in our previous proposal, the PSG, interventions, and laboratory measures were going to be conducted off-site at USC.

The intervention will be more conducive to exercise and weight loss than is typical, which will limit the study’s generalizability. Presently, we believe it is most imperative to establish efficacy. As exemplified by the VA “Move!” program, there is an accelerated focus on exercise and weight loss which could facilitate these behaviors among veterans with OSA at no cost. Subsequent studies could compare lab vs. home intervention.

Follow-up assessments will be influenced by uncontrolled factors, e.g., the extent to which participants maintain or initiate exercise, weight loss, or PAP. Ethics dictate allowing post-study treatments. Careful assessment of these should permit some conclusions regarding the chronicity of post-treatment improvements.

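### The stated 22-23 participants a year does not deliver 90 within the 44-month data-collection window, and it conflicts with the plan's monthly-wave schedule

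*Combined protocol and SAP*

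**What the plan says.** Section 5.1 sets the size and length of the trial: "The proposed 4-year randomized controlled trial will assess N=90 veterans (ages 18-60 years) with OSA". It then gives the annual throughput, "Each year, 22-23 participants will be assessed in 18-week cycles, including screening, baseline, and a 16-week intervention", and adds: "Follow-up assessments will continue for 3 months after the intervention".

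Section 5.12 divides the four years differently. The first 2 months are for equipment purchases and the final 2 for analysis and manuscripts. In between, "Data collection is expected to take 44 months". The same section describes entry as rolling: "Baseline assessments should begin by the end of Month 2, and baseline assessments of new waves of participants will occur monthly", and as an aim, "we will strive to schedule waves of ≥ 5 participants".

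Section 5.9 bases power on 30 participants per arm. For the primary comparison it states 86%, or 82.2% after 10% attrition. Under section 5.10, the 3-month follow-up is the endpoint of Secondary Hypothesis 1 only. The Primary Hypothesis and Secondary Hypothesis 3 use the immediate post-test, and Secondary Hypothesis 2 compares pre- with post-treatment.

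**The concern.** An annual target is what a site and its monitors measure progress against. Here the target equals N divided by the whole length of the study, so it assumes that participants enter, and count, in all 48 months. Four of those months are reserved for other work. A participant who enters late in the remaining 44 cannot finish treatment, let alone follow-up, before data collection ends.

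A site that met 22-23 each year would therefore look on schedule and still fall short of 30 per arm when the window closed. The other accrual statement, monthly waves of at least 5, implies a pace more than twice as fast. The plan gives no last-entry date that would show which pace is intended. At stake is the power claimed for the primary comparison and, more so, for the follow-up comparison, which section 5.9 already treats as the weaker one.

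**Working it through.** **Inputs.** N = 90, 22-23 per year, an 18-week cycle and 3 months of follow-up (5.1). Two start-up months, 44 months of data collection, 2 closing months, and monthly waves with an aim of at least 5 (5.12). Difference 4, SD 5, alpha 0.025, 30 per arm, 10% attrition (5.9). Assumptions made here: even entry from the start of the 44 months, and 52.18 weeks per year.

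**Step 1: the plan's own figure.** 22 × 4 = 88, 22.5 × 4 = 90 and 23 × 4 = 92. The annual rate reproduces 90 only if all 48 months count. The calendar is 2 + 44 + 2 = 48.

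**Step 2: time needed per participant.** To the post-test: 18 × 12/52.18 = 4.14 months. To the 3-month follow-up: 4.14 + 3 = 7.14 months.

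**Step 3: participants at the stated rate.** Number = rate × entry months/12.

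| Requirement | Entry months | At 22/yr | At 23/yr | Rate needed for 90 |
|---|---|---|---|---|
| Entry in all 44 months, outcomes ignored | 44 | 80.7 | 84.3 | 24.5/yr |
| Post-test inside the 44 months | 44 − 4.14 = 39.86 | 73.1 | 76.4 | 27.1/yr |
| 3-month follow-up inside the 44 months | 44 − 7.14 = 36.86 | 67.6 | 70.6 | 29.3/yr |
| Follow-up allowed to use the 2 closing months | 46 − 7.14 = 38.86 | 71.2 | 74.5 | 27.8/yr |

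No row reaches 90. These are entrants before attrition. After 10% attrition, 73-76 becomes about 66-68 and 68-71 becomes about 61-64, against 90 × 0.9 = 81.

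**Step 4: last entry.** Entry opens at the end of Month 2. For all follow-up to fall inside the window it must close at 2 + 36.86 = 38.9, about Month 39.

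**Step 5: the other accrual statement.** Five per month × 12 = 60 a year, and 90/5 = 18 months to fill the trial. At 22-23 a year, a monthly wave would hold about two participants (22.5/12 = 1.9).

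**Step 6: power.** Two-sample t-test with noncentrality = 4/(5 × √(2/n)) and 2n − 2 degrees of freedom. Section 5.9 does not say whether the 0.025 is one- or two-sided. One-sided 0.025 gives 86.1% at n = 30 and 82.2% at n = 27, which match the stated figures. Two-sided 0.025 gives 78.5% and 73.5%, which do not. With the one-sided version that reproduces the plan:

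| Entrants | Per arm | Power | Power after 10% attrition |
|---|---|---|---|
| 90 | 30 | 86.1% | 82.2% |
| 76 | 25.3 | 79.7% | 75.2% |
| 73 | 24.3 | 78.0% | 73.4% |
| 71 | 23.7 | 76.8% | 72.2% |
| 68 | 22.7 | 75.0% | 70.2% |

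The 73 and 76 rows apply to the primary comparison and the 68 and 71 rows to Secondary Hypothesis 1. Section 5.9 also considers a follow-up effect 80% as large (4 × 0.8 = 3.2) and gives about 65%. The same method gives 63.6% at 27 per arm, and 51-53% at 68-71 entrants after 10% attrition.

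**The case against.** The strongest reply is that 22-23 is a rounded planning average and not a cap. N = 90 and 30 per arm are stated repeatedly, and nothing says that enrolment closes short of them. The section that sets the 44 months also plans monthly waves, and at 5 per wave the trial would fill in 18 months. The 44 months is itself only an expected duration.

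Much of this stands. A reader might infer that the trial will end with 68-71 participants, or that late follow-ups will be cut off. The documents support neither: the count is conditional on constant entry at the stated rate, and no truncation rule is given. A reader might also carry 68-71 over to all the hypotheses, but it bears on Secondary Hypothesis 1 alone.

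It is also fair to say that the 18-week cycle includes screening, some of which could precede the first baseline. Counting only the 16 treatment weeks would add 2 × 12/52.18 = 0.46 months of entry, less than one participant at 23 a year.

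Finally, one might want to correct the remark in section 5.13, "We would need to recruit only 2% of these cases if this was our only source of subjects". That does not follow. At 25 new cases a week (25 × 52 = 1,300 a year), 29.3 a year is 2.25%, which rounds to 2%.

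What the reply does not remove is the conflict. An average over four years still needs entrants in months when they cannot finish. The wave size is something the team hopes for; if met, it is about 2.7 times the stated annual rate (60/22.5). The only past accrual in the documents, 43 participants over 2 years (5.13), is 21.5 a year, close to the slower figure. Section 5.13 gives reasons to expect better but no rate.

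**Conclusion.** The concern holds as an inconsistency among the plan's accrual statements and its calendar. The 22-23 a year makes no allowance for start-up, close-out or the time a participant needs to reach an endpoint, and no reading of it over the 44 months gives 90. A site meeting that target exactly would fall about 14-17 participants short of 90 at the post-test and about 19-22 short at the 3-month follow-up. Power for the primary comparison would fall from 86% to about 78-80%, or from 82.2% to about 73-75% after attrition.

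These sizes assume even entry at the stated rate, outcomes collected inside the 44 months, and the one-sided test that reproduces the plan's power. They are not a forecast of the final sample: the monthly waves, if filled as hoped, would avoid any shortfall. Power for Secondary Hypotheses 2 and 3 was not recomputed; they share the post-test count of 73-76. The planning figure should be corrected, but this is not a flaw in the design or the analysis.

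**What to change.** - In 5.1, replace 22-23 per year with a minimum enrolment rate that delivers 90 inside the window. The exact requirement is 29.3 a year (about 2.4 a month), so about 29-30; at 30 a year, 36.86 months gives 92.
- In 5.12, state a last-entry date of about Month 39, so that every 3-month follow-up falls inside the 44 months.
- In 5.12, reconcile the monthly-wave statement with that minimum without slowing it, for example by presenting the annual rate as the floor and the wave size as the aim.

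The 2% remark in 5.13 can stay as it is.

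The cost is protocol wording and a revised recruitment target. N, randomisation and analysis are unchanged. The downside is a target pace about 30% faster than the one now stated (29.3/22.5 = 1.30), and about 36% above the previous trial's 21.5 a year (29.3/21.5 = 1.36).

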5.5. Treatment Randomization, Instructions, Adherence Strategies. Following baseline, participants will be randomized to one of three 16-wk treatments: (1) **Exercise Alone** (n=30) (**5.5.1**); (2) **Weight Loss Alone** (n=30) (**5.5.2**); or (3) **Exercise + Weight Loss** (n=30) (**5.5.3**). Randomization will be stratified by age (< vs. ≥ 40), sex, and severity of screening AHI (10-25 or > 25) in blocks of 6, using a computer-generated list.

The duration of the intervention was chosen so that there would be sufficient time to detect chronic adaptations to the interventions without placing undue burden on the participants. Sixteen weeks is sufficient time to detect chronic exercise benefits¹⁴ and to achieve the targeted weight loss using the moderately challenging proposed procedures. Following randomization, treatment expectancy for changes in OSA severity, sleep quality, daytime sleepiness, mood, and health will be assessed via 5-point Likert scales.

Lifestyle Activity and Eating. Because lifestyle changes could mask the effects of the experimental exercise and weight loss, participants will be asked to maintain their normal activity and eating habits, except as prescribed for the study. In our previous trial, such requests were followed, as evidenced by the lack of weight loss¹⁹ and the proposed monitoring methods.

To monitor changes in unsupervised physical activity, participants will wear a waist accelerometer from baseline through the post-intervention assessment (except during experimental exercise). This device has been validated against energy expenditure estimated with oxygen consumption and doubly labeled water. It records daily steps and time spent in light, moderate, and vigorous activity. Data will be analyzed in 2-wk bins.

Food intake will be assessed with the Automated Self-Administered 24-hr diet recall (ASA24) (<http://riskfactor.cancer.gov/tools/instruments/asa24/>), to be completed twice during baseline and during Weeks 8 and 16 of treatment. The recall is among the highest quality with the least bias and subject burden.

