Adherence Strategies. Adherence will be promoted with a personalized approach to the intervention. One staff member will serve as the principal contact for each participant. In our experience, participants prefer to work with one person to make appointments, etc. Staff will be trained to develop rapport with the participant by discussing expectations of the participant's and staff's roles. We have found that personalizing this relationship in a professional context enables participants to be more direct about problems, thus enabling a strong foundation for problem solving. Prior to randomization, staff will share expectations regarding study attendance requirements and will ask participants about their expectations regarding randomization. During pre-randomization visits, we will ask participants whether they can make this type of commitment. If they cannot, we will exclude them. If they believe they can, we will ask them to sign a contract that affirms their commitment to attend their scheduled exercise and diet counseling. If participants are nonetheless unable to attend scheduled appointments, we will ask them to call as far as possible ahead of time to reschedule. If a participant misses an exercise session, his/her assigned staff will call to check-in, encourage attendance, and help

troubleshoot barriers. The VA Exercise Center (EC) will be open 7 days per week for 15 h/day to accommodate a variety of schedules. Because it is unrealistic to expect 100% adherence to the exercise protocol, unforeseen circumstances (e.g., an unexpected trip out of town) might prevent an individual from coming to the EC but might still allow him/her to continue to exercise. In these situations, we will provide the participant with a Polar HR monitor and instruct him/her how to keep his/her HR at the desired level for the required number of minutes. We will have precise data from the participant's laboratory exercise sessions and can use this information to develop a specific and accurate exercise prescription. In these situations, we will also ask participants to keep a diary of the frequency/duration of these sessions. We will download data from the HR monitor to confirm the diary data. Similar accommodation for missing the nutritional counseling will be arranged. If necessary, up to two counseling sessions will occur via telephone. We will allow four unsupervised exercise sessions throughout the trial. In addition, the run-in and incentives will help ensure adherence.

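### With visible treatments at one site and a fixed block size of 6, staff who track assignments could be certain of about 1 in 6 of them, and section 5.5 states no concealment safeguard

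*Combined protocol and SAP*

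**What the plan says.** Section 5.5 puts allocation after the baseline week: "Following baseline, participants will be randomized to one of three 16-wk treatments". The arms have 30 participants each. The list is stratified by age (below 40, or 40 and over), sex and screening AHI (10-25, or above 25), and is generated "in blocks of 6, using a computer-generated list". That is the whole description. It does not say who holds the list, how or when an assignment is released, whether the block size is withheld from staff, or whether enrolling and treating staff are different people.

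Under Adherence Strategies in the same section, "One staff member will serve as the principal contact for each participant". Staff set out the attendance requirements and discuss expectations about randomization, and then: "During pre-randomization visits, we will ask participants whether they can make this type of commitment. If they cannot, we will exclude them". Those who believe they can commit sign a contract.

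Section 5.13 states that "the entire study will be conducted at the Phoenix VA". Sections 5.5.1 to 5.5.3 have study staff deliver the supervised exercise and the diet counselling. Blinding is stated for outcome measurement: actigraphy and diary averaging and PSG measures (5.6.1), laboratory assessments (5.6.2) and questionnaires (5.6.3). None is stated for enrolment.

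**The concern.** A treatment that staff can see, combined with one fixed block size, lets the sequence be partly reconstructed. Anyone who knows the earlier assignments in a stratum can count what is left in the block. All three stratification factors are known before randomization, so the candidate's stratum is known too.

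This matters here because an exclusion step based on commitment comes before allocation, and the arms differ greatly in what they ask. Exercise is 4 sessions a week for 16 weeks, or 64 sessions. Weight loss is 16 weekly counselling sessions. The combination is 64 + 16 = 80. The primary hypothesis (5.9) is that the combination arm does better than each single arm. If someone expecting the next slot to be the combination arm discouraged or deferred a doubtful candidate, that arm would gather more committed participants and the primary contrast would tend to favour it. Blinded PSG scoring cannot correct a difference present before treatment starts.

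**Working it through.** The documents give no predictability figure, so there is none to reproduce. The check asks what a person who knows the block size and the earlier assignments in a stratum can deduce.

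**Inputs.** Three arms, block size 6 and 30 per arm (5.5), hence 2 of each arm per block; N = 90 (5.1); 2 × 2 × 2 = 8 strata (5.5).

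**One complete block.** There are 6!/(2!·2!·2!) = 90 equally likely orderings.

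| Position | Next arm certain | At least one arm ruled out | Best guess right |
|---|---|---|---|
| 1 | 0 | 0 | 1/3 = 0.333 |
| 2 | 0 | 0 | 2/5 = 0.400 |
| 3 | 0 | 1/5 | 2/4 = 0.500 |
| 4 | 0 | 3/5 | 0.4 × 1/3 + 0.6 × 2/3 = 0.533 |
| 5 | 1/5 | 1 | 0.2 × 1 + 0.8 × 1/2 = 0.600 |
| 6 | 1 | 1 | 1.000 |
| Mean | 1.2/6 = 20.0% | 2.8/6 = 46.7% | 3.367/6 = 56.1% |

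The fifth assignment is certain when the last two slots belong to the same arm, which has probability 1/5. After three assignments all arms are still equally open with probability 4/5 × 2/4 = 0.4; otherwise one arm is used up. Chance guessing is right 33.3% of the time.

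**Eight strata, 90 participants.** Last blocks are usually incomplete, which removes some of the predictable late positions. A stratum that stops at 11 has (1.2 + 0.2)/11 = 12.7% certain; one that stops at 12 has 2.4/12 = 20%. The documents do not give the stratum mix, so it was assumed, and stratum sizes were simulated.

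| Assumed mix | Certain | At least one arm ruled out | Best guess right |
|---|---|---|---|
| Eight equal strata | 15.9% | 40.4% | 53.2% |
| Factor splits 40/60, 80/20, 50/50 | 15.7% | 40.2% | 53.1% |
| Factor splits 25/75, 90/10, 50/50 | 16.3% | 40.6% | 53.3% |
| Factor splits 20/80, 95/5, 60/40 | 17.0% | 41.7% | 53.8% |

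Splits are for age, sex and screening AHI in that order. In participants, 0.157 × 90 = 14.1 to 0.170 × 90 = 15.3.

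**Randomly varying block sizes, unknown to staff (simulated).**

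| Setting | Block sizes | Certain | At least one arm ruled out | Best guess right |
|---|---|---|---|---|
| Single list of 90 | fixed 6 | 20% | 47% | 56% |
| | 3, 6, 9 | 3.8% | 10.4% | 55.2% |
| | 6, 9 | 4.9% | 13.3% | 53.9% |
| Stratum of 11 | fixed 6 | 12.7% | 41.8% | 52.1% |
| | 3, 6, 9 | 2.6% | 7.9% | 52.0% |
| | 6, 9 | 4.3% | 12.2% | 50.4% |

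Varying sizes remove most of the certainty but barely change how often a best guess succeeds.

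**The case against.** Several points on the other side have force.

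- **Silence is not disclosure.** Nothing shows that staff can see the list or would track assignments by stratum. Each participant has one principal contact, and no single person is said to see a whole stratum's sequence. This stands, and it is why the figures are conditional.
- **The exclusion rests on the participant's own answer.** A reader might infer that staff make a subjective commitment judgement immediately before allocation. The text does not support that: the question is put at undated visits before randomization, the run-in precedes baseline (5.3.1.5), and a baseline PSG with its own AHI exclusion follows (5.6.1). What remains is that staff frame the question, hear the answer and act on it, and no order of events is fixed.
- **Swapping candidates is hard at this accrual rate.** With 22-23 participants a year (5.1) and eight equal strata (assumed), 22.5/8 = 2.8 per stratum per year, or about one every four months. If one stratum held half the sample (also assumed), it would be about one a month. Within a wave (5.12), the order of randomization may be unknown when commitment is asked. This limits swapping; discouraging or deferring one candidate needs no second person.
- **Everyone is screened against the full burden.** Table 1 requires acceptance of any assignment, and the contract covers both exercise and diet counselling. This narrows the range of commitment left to select on, but does not remove it.
- **The ANCOVA (5.10) adjusts for percentage of sessions attended.** That variable arises after randomization and does not measure motivation or dietary adherence, so it cannot undo selection before allocation. Adjusting for baseline AHI, age and sex does not capture commitment either.

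**Conclusion.** The concern holds as a vulnerability in the stated method that is cheap to remove. With eight strata, about 1 in 6 assignments (about 14 to 15 of 90) could be certain in advance, at least one arm ruled out for 40% to 42%, and a best guess right 53% to 54% of the time. In complete blocks on a single list the figures are 20%, 47% and 56%. All assume that staff know the block size and follow assignments by stratum; the eight-stratum figures also rest on assumed mixes.

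Two stronger readings are not supported. A reader might infer that upcoming assignments can often be worked out, or that 18 of 90 would be known. The latter ignores stratification and incomplete last blocks, and for most assignments the knowledge is partial at best. A reader might also infer that the primary comparison will be biased towards the combination arm. The documents show that such selection is possible, not that it would happen. Its direction depends on staff motives, and its effect on AHI cannot be derived from the plan.

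**What to change.** Amend section 5.5 in two steps, in this order of importance.

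1. State that each assignment is released only after eligibility, the baseline PSG result, the commitment answer and the signed contract have been recorded and locked. The list should be held and released by the biostatistician or another person outside enrolment and treatment. This is the main protection, because it works however well the next assignment can be guessed: the decision to enrol can no longer be revised once the assignment is known, and is documented before release. To limit guessing beforehand, the commitment answer should be recorded when it is given.
2. Replace the fixed block of 6 with randomly varying block sizes within each stratum, for example 3, 6 and 9, or 6 and 9. Keep the sizes in a document that enrolling and treating staff do not see. On a single list this cuts certain assignments from 20% to about 4% to 5%, but leaves the best-guess rate at about 54% to 55%, so it should not stand alone.

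The cost is a regenerated list and a short addition to 5.5, with no change to sample size, treatments or visits. The downside is slightly larger possible imbalance within small strata: the widest gap between two arms inside an unfinished block rises from 2 (block of 6) to 3 (block of 9).
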